6 STUDY DESIGN AND PROCEDURES

- Study design
 - The study will use a difference-in-differences design in which changes before and after the intervention will be compared between a treatment group and a control group.
 - The treatment group will include all patients undergoing tonsillectomy at C.S. Mott Hospital by a pediatric otolaryngology faculty member at the University of Michigan.
 - The control group will include all patients undergoing tonsillectomy at University Hospital, Brighton Center for Specialty Care, or Livonia Center for Specialty Care by a general otolaryngology faculty member at the University of Michigan.
- Data collection procedures throughout the study
 - There will be three sets of surveys: a baseline survey, daily surveys on post-operative days 1-13, and a final survey on post-operative day 14. Post-operative surveys will be sent to all patients who enroll, including those who are not prescribed opioids post-operatively. These patients will not be included in the primary or secondary analysis but will be analyzed in a separate study examining pain recovery without opioids.
 - Baseline survey: Patients will be asked to complete a 10-15 minute survey assessing demographics, reason for tonsillectomy, current pain, chronic pain, history of opioid use, history of opioid misuse, family chronic opioid use, depression, substance use disorders, anxiety, sleep, and global health. Patients will be e-mailed a link to the baseline survey upon enrollment; for patients who cannot receive e-mail links, the survey will be administered over the phone. For patients at Mott or University Hospital recruited in-person, the baseline survey will be administered by a study team member in-person through Qualtrics on a tablet. Patients sent the baseline survey who do not complete it before surgery will be contacted via e-mail or by phone to remind them or approached in-person to complete it through Qualtrics on a tablet. If patients are contacted by phone, they will be given the option to complete the survey over the phone.

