- Daily surveys: At 12:01 am on post-operative days 1 through 13, patients will be e-mailed a daily link to complete a 1-minute online Qualtrics survey in which pain and opioid consumption over the prior 24 hours will be assessed. The post-operative day 7 survey will be similar except that it will include additional questions assessing pain over the prior 7 days. Patients who cannot receive e-mail links will not be sent daily surveys. E-mail or telephone follow-up will not occur for the daily surveys on post-operative days 1-13.
 - Final survey: on post-operative day 14, patients will be e-mailed a link to complete a 10-15-minute online Qualtrics survey assessing pain control, opioid use, opioid disposal, opioid misuse, acetaminophen/ibuprofen use, depression, anxiety, sleep, and health care utilization during the 14 days after surgery, including refills and visits to the emergency department or primary care for pain. Patients who cannot receive e-mail links will be called and the survey will be administered over the phone. Patients may be contacted via e-mail or by phone to remind them to complete surveys. If patients are contacted by phone, they will be given the option to complete the survey over the phone.
 - DataDirect and MiChart will be queried to determine opioid use prior to the day of surgery based on the admission history and physical, patient demographics, the dosing parameters of post-operative opioid prescriptions, the number of return visits for pain at the University of Michigan in the 14 days after surgery, and the number of opioid refills in the 14 days after surgery.
- Timeline
 - The pre-intervention period will start on October 1, 2019 and end September 30, 2020; the months of April and May 2020 will be excluded as elective surgeries were scaled down owing to the COVID-19 pandemic. The intervention will be implemented on October 1, 2020. The post-intervention period will start October 1, 2020 and end on July 31, 2021.
 - Nature of intervention
 - Currently, pediatric otolaryngology attendings and their residents use a MiChart tonsillectomy orderset with three options: patients < 12 years, patients ≥12 years, and M-POP. Under the orderset for patients ≥12 years, the default is currently 30 doses, consistent with the current departmental prescribing standard (see MiChart screenshot below).
 - During the pre-intervention period, no changes will be made to the default number of doses or any other dosing parameter.

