 - During the month of September 2020, opioid consumption data will be reviewed by the chief of pediatric otolaryngology. A new default

- number of doses lower than 30 will be chosen based on the level and distribution of opioid consumption.
- On October 1, 2020, the tonsillectomy orderset will be changed. The new orderset will have three options for patients ≥ 12 years: one for oxycodone solution among patients < 50 kg, one for oxycodone solution among patients ≥ 50 kg, and one for oxycodone tablets. Each of these options will auto-populate the default doses field using the new setting.
 - The new orderset will display for patients at C.S. Mott Hospital only. Thus, all patients in the treatment group (patients undergoing tonsillectomy at Mott by pediatric otolaryngology attendings) will have clinicians who are exposed to the new default settings. The tonsillectomy orderset will not be changed at University Hospital, Brighton, or Livonia. Thus, all patients in the control group (patients undergoing tonsillectomy in these locations by general otolaryngology attendings) will have clinicians who will not be exposed to the new default settings, even if they use the pediatric otolaryngology tonsillectomy orderset.

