- Data from the daily surveys will be used to assess whether daily opioid consumption reports matches the consumption reported on the final post-operative day 14, and will also be analyzed in a separate study assessing the trajectory of pain and opioid use after tonsillectomy.
- We will fit linear or logistic regression models assessing outcomes as a function of an indicator of post-intervention status, an indicator of treatment group status, and its interaction, controlling for covariates such as demographics (e.g., age, sex) and baseline co-morbidities (e.g., depression, anxiety). We will graphically and statistically assess the comparability of pre-intervention monthly trends in outcomes between the treatment and control groups.

- We hypothesize that there will be no change in outcomes in the control group (i.e., that the post-intervention trend in outcomes in the control group will be an extension of the pre-intervention trend in outcomes). In contrast, we hypothesize that the number of doses and opioid consumption will drop in the treatment group after the intervention; that the proportion of patients with prescriptions concordant with the new defaults will increase after the intervention; and that there will be no change in balancing measures such as pain control or depression.
- Sensitivity analyses
 - Statistical modeling: we will explore whether results change when replacing the indicator of treatment group status with a vector of fixed effects for the prescribing clinician, and will explore the feasibility of using an interrupted time series approach instead of a difference-in-differences approach.
 - We will determine whether any otolaryngology residents wrote opioid prescriptions for both a pediatric otolaryngology and general otolaryngology patients in the post-intervention period, and exclude data from any such residents from the analysis
 - We will exclude opioid prescriptions written for patients of the chief of pediatric otolaryngology, who will be involved in setting the new defaults
- Subgroup analysis will occur by age group (ages 12-17 years vs 18 and older), gender, payer type (private/public), and baseline co-morbidities (e.g., depression and anxiety).
- We will separately analyze data from pediatric otolaryngology patients undergoing surgery outside of Mott and general otolaryngology patients undergoing surgery at Mott to assess for any spillover effects.

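### If the undefined prescribing clinician includes residents who cross groups, the exploratory fixed-effects check that drops the treatment indicator can show a persistent group difference as an intervention effect (minor).

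*Combined protocol and SAP*

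**What the plan says.** The main model in section 10 regresses each outcome on "an indicator of post-intervention status, an indicator of treatment group status, and its interaction", plus covariates such as demographics and baseline co-morbidities. Under the sensitivity analyses, "we will explore whether results change when" "replacing the indicator of treatment group status with a vector of fixed effects for the prescribing clinician". That model therefore has clinician effects, post and the post-by-treatment interaction, with no treatment main effect.

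The plan does not say who the prescribing clinician is. Section 6 defines the groups by site and by the attending's service; treated patients, for example, are operated on "by a pediatric otolaryngology faculty member at the University of Michigan". Section 6 also says that "pediatric otolaryngology attendings and their residents use a MiChart tonsillectomy orderset", so residents prescribe too. A separate sensitivity analysis looks for residents who wrote prescriptions "for both a pediatric otolaryngology and general otolaryngology patients in the post-intervention period, and exclude data from any such residents from the analysis". It is not said to be combined with the fixed-effects check.

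**The concern.** Clinician effects make the treatment indicator redundant only when each clinician belongs to one group in both periods. Once a clinician appears in both groups, the interaction is the only term left that can represent a treated-control contrast within that clinician. A constant difference due to site, service, orderset use or unadjusted case mix then loads onto the interaction although nothing changed in October 2020.

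The check is there to show whether the main finding is robust. If the same clinician wrote more doses for treatment-group patients at baseline, the leak hides part of a real reduction. If fewer, it imitates one. Either way the two analyses could differ for a reason unrelated to the new default.

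**Working it through.** **Inputs from the documents.** Section 10 expects 113 + 85 = 198 patients in the primary analysis, which reproduces the stated total. The pre-period runs from October 2019 to September 2020, and "the months of April and May 2020 will be excluded", which leaves 10 months. October 2020 to July 2021 is also 10 months. With steady volume, the post-period share of patients is q = 10/20 = 0.5. The plan gives no figure for this check.

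**Assumptions not in the documents.** The crossing shares; 12 residents; a linear outcome; no covariates; and, for precision only, residual SD 1 and clinician SD 0.375.

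**Step 1: hand example (illustrative doses).** One resident writes equally for both groups in both periods. There is no intervention effect and a constant gap of 5. Cell means are 10 (control, pre), 15 (treated, pre), 10 (control, post) and 15 (treated, post).
- As written, the two pre cells share one fitted value, 12.5, and the interaction is 15 - 10 = 5. The whole gap appears as an effect.
- With the indicator kept, the interaction is (15 - 15) - (10 - 10) = 0.
- With a true effect of -10, treated post is 5. As written the interaction is 5 - 10 = -5; with the indicator kept it is (5 - 15) - (10 - 10) = -10.

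**Step 2: residents writing for both groups in both periods.** Let s be their share of prescriptions, the same in each group and period. Regressing the omitted indicator on post and post-by-treatment within clinician gives

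leak / gap = s / (1 - q(1 - s)), which is 2s / (1 + s) at q = 0.5.

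| s | q = 0.5 | Simulated, q = 0.5 | q = 0.4 | q = 0.6 |
|---|---|---|---|---|
| 10% | 0.20/1.10 = 0.18 | 0.16-0.18 | 0.10/0.64 = 0.16 | 0.10/0.46 = 0.22 |
| 25% | 0.50/1.25 = 0.40 | 0.39-0.41 | 0.25/0.70 = 0.36 | 0.25/0.55 = 0.45 |
| 50% | 1.00/1.50 = 0.67 | 0.66-0.68 | 0.50/0.80 = 0.63 | 0.50/0.70 = 0.71 |

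The simulations used 113 + 85 patients and a true effect of 0.

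**Step 3: residents changing group between periods.** If equal numbers move in each direction, groups and periods are balanced, and the movers hold share w of prescriptions, the same algebra gives leak / gap = 2w. For 2 of 12 residents this is 2 × 2/12 = 0.33 (simulated 0.33-0.34). One resident of 12 moving in one direction only gives 0.16. None of these residents writes for both groups after October 2020, so the plan's exclusion leaves these figures unchanged.

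**Step 4: residents crossing only before October 2020.** If they have no post-period prescriptions, post and post-by-treatment are both zero for all their patients. They carry no information on the interaction, and the leak is exactly 0. If they go on prescribing for one group, the leak is not zero. Its size depends heavily on the assumed layout, so no figure is given.

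**Step 5: what removes the leak.** A group difference that is only the clinicians' own habits leaks 0. With the indicator kept, the leak was 0.00 in every scenario where the interaction could be estimated. Combining the check as written with the plan's exclusion brings Step 2 to 0.00-0.03, but does nothing for Step 3.

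**Step 6: precision (SD of the interaction estimate).**

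| Scenario | As written | Indicator kept | Ratio | Main model |
|---|---|---|---|---|
| s = 10% | 0.290 | 0.302 | 1.04 | 0.312 |
| s = 25% | 0.266 | 0.297 | 1.12 | 0.307 |
| s = 50% | 0.242 | 0.291 | 1.20 | 0.301 |
| 2 of 12 swap | 0.299 | 0.326 | 1.09 | 0.355 |
| 4 of 12 swap | 0.297 | 0.368 | 1.24 | 0.393 |

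**The case against.** Three conditions must hold together, and the documents establish none of them: residents count as the unit, some of them cross, and a gap persists within clinician. Section 10 says only that the team will find out whether any resident crossed. The gap may be small: section 6 describes a 30-dose departmental standard and allows that control clinicians are unexposed to the new default "even if they use the pediatric otolaryngology tonsillectomy orderset". The models also adjust for age and co-morbidities, so only the remaining gap can leak. All of this stands, and it keeps the point minor.

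There is also a bias-variance argument. From the SDs and leaks above, the check as written has the lower mean squared error when the gap is below √(0.302² - 0.290²)/0.18 = 0.47, √(0.297² - 0.266²)/0.40 = 0.33 or √(0.291² - 0.242²)/0.67 = 0.24 residual SD, at 10%, 25% and 50% crossing. The arithmetic is right. But a difference-in-differences design is chosen so that a baseline gap need not be small, and its robustness check should not bring that condition back.

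A reader might infer that, when the two analyses disagree, the main result is the correct one. The documents do not support that. When residents swap groups, their habits move with them and enter the main model. With clinician SD 0.375 and 2 of 12 swapping, this adds error with SD about 0.21 residual SD to the main estimate and none to the check as written. A disagreement could therefore be the check correcting the main model.

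**Conclusion.** The point holds conditionally and is minor. With attendings as the unit, the check is sound. With residents as the unit and crossing that involves post-period prescriptions, it passes on part of any within-clinician group difference left after adjustment: about 0.16-0.18, 0.40 and 0.67 of it at assumed shares of 10%, 25% and 50%, and about a third if 2 of an assumed 12 swap groups. These fractions rest on a linear outcome, equal periods and the assumed crossing patterns. Logistic outcomes were not quantified, and no size in doses can be given.

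Two stronger readings are tempting and unsupported. One is that the main difference-in-differences estimate has this leak; it does not, because it keeps the indicator. The other is that the leak is likely to match or exceed the whole group difference. The algebra allows that when half or more of the residents swap groups, but nothing in the documents suggests swapping on that scale.

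**What to change.** 1. In this check, add the clinician fixed effects to the treatment indicator, post and the interaction instead of replacing the indicator. If clinicians are nested, the indicator drops out by itself and the estimate is unchanged.
2. State whether the prescribing clinician is the attending or the person who signs the discharge prescription.
3. Tabulate residents by group and period, so that crossing within and between periods is visible.

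The cost is one model term, one definition and one table. If residents cross, this exploratory check becomes less precise: the SD is about 4-20% larger at 10-50% crossing, and more with heavy swapping (24% with 4 of 12). In these scenarios it is still about as precise as the main model. Relying instead on the plan's exclusion within the check costs more (SD 4%, 15% and 41% above the indicator-kept version at 10%, 25% and 50%) and still misses residents who change group between periods. If every resident swaps groups, the interaction cannot be estimated in this check, and the report should say so.

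### The contamination check selects prescribers by role and service, but the new default displays by hospital, so control prescriptions by exposed prescribers can go unflagged

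*Combined protocol and SAP*

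**What the plan says.** Section 6 (Study Design and Procedures) makes display of the changed orderset depend on where the patient is treated: "The new orderset will display for patients at C.S. Mott Hospital only". Treatment patients are those operated on at Mott by pediatric faculty. Controls are "patients undergoing tonsillectomy at University Hospital, Brighton Center for Specialty Care, or Livonia Center for Specialty Care by a general otolaryngology faculty member". Hospital and service must therefore both match before a patient falls in either group. The same section says that all control patients "will have clinicians who will not be exposed to the new default settings, even if they use the pediatric otolaryngology tonsillectomy orderset". On current use of the orderset it says that "pediatric otolaryngology attendings and their residents use a MiChart tonsillectomy orderset".

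Section 10 (Statistical Considerations), under sensitivity analyses, looks for prescribers who span the two groups. The rule covers residents only and is set by service: "We will determine whether any otolaryngology residents wrote opioid prescriptions for both a pediatric otolaryngology and general otolaryngology patients in the post-intervention period". The action is to "exclude data from any such residents from the analysis". The only exclusion at attending level concerns the treatment side: "We will exclude opioid prescriptions written for patients of the chief of pediatric otolaryngology". Section 10 also plans a separate analysis of patients outside both groups, namely pediatric-service patients operated on elsewhere and "general otolaryngology patients undergoing surgery at Mott to assess for any spillover effects".

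**The concern.** A contamination check should select on what causes contamination. Here that is having met the new default, which can happen only when ordering for a Mott patient. The planned rule selects on two other attributes: being a resident, and having written for both services.

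The control group's surgeons are general-service faculty, and the plan foresees general-service patients at Mott. Prescribers from the control group's own service may therefore meet the new default there. A resident who does so and also writes for controls need never write for a pediatric-service patient, and so need never satisfy the rule. An attending is outside the rule altogether.

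Section 10 hypothesizes no change among controls. If carry-over lowers control quantities, the difference-in-differences subtracts that fall as if it were background trend. The estimated effects on number of doses and on concordance with the new default then shrink. This sensitivity analysis is where a reader would look for reassurance. If it keeps the same prescriptions, its agreement with the main result says nothing about this route.

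**Working it through.** **Step 1. Apply the planned rule to each type of prescriber.** The rule is from section 10 and the display condition from section 6. All four types are hypothetical; the documents give no counts for any of them.

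| Prescriber, post-intervention | Can have met the new default? | Flagged by planned rule? |
|---|---|---|
| Resident: general-service patients at Mott and at a control site | Yes | No |
| General-service attending: writes at Mott and at a control site | Yes | No |
| Resident: pediatric-service patients at Mott, general-service controls | Yes | Yes |
| Resident: pediatric-service patients only outside Mott, general-service controls | Not through the display | Yes |

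The rule misses the first two types, catches the third, and can remove the fourth needlessly.

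**Step 2. Ask whether another planned analysis closes the gap.**

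- The spillover analysis studies patients outside both groups. It does not ask who wrote the control prescriptions.
- Clinician fixed effects absorb stable differences between prescribers, not a change in one prescriber's habit after meeting the default.
- Excluding the pediatric chief's patients acts on the treatment group.
- An interrupted time series, whose feasibility is to be explored, could be run without controls. It would then be a different analysis and would leave the difference-in-differences as it is.
- The main model has no prescriber-level exclusion.

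**Step 3. Size, on assumed inputs.** The plan's own figure reproduces: 113 + 85 = 198 patients for the primary analysis. Section 10 states no power, effect size or standard deviation.

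Let D be the true effect and g the common trend. Let m be the share of post-intervention control prescriptions written by exposed prescribers whom the rule does not flag, and k the fraction of the effect they carry over.

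- Change in treatment group: g + D
- Change in control group: g + m × k × D
- Difference-in-differences: D × (1 − m × k)

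Both study periods contain 10 months once April and May 2020 are left out. With an even split, assumed here, there are 85 / 2 = 42.5 post-intervention controls.

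| m (assumed) | Control prescriptions (m × 42.5) | Effect kept, k = 0.5 | Effect kept, k = 1 |
|---|---|---|---|
| 5% | 2.1 | 97.5% | 95% |
| 10% | 4.2 | 95% | 90% |
| 20% | 8.5 | 90% | 80% |
| 30% | 12.8 | 85% | 70% |

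About four control prescriptions therefore make up a 10% share. The planned exclusion leaves the loss from this source in place.

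**The case against.** **Crossover is not documented.** A reader might infer that attendings do cross between sites and that exposed prescribers are in the control group. The documents do not support that. They foresee general-service patients at Mott, but do not say that the same individuals also prescribe for controls, how often they would, or how often attendings write prescriptions themselves. This stands, and it limits the point to what the rule could miss.

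**Section 6 need not contradict section 10.** A reader might take the statement that control clinicians are unexposed as disproved by the expected general-service cases at Mott. It can also mean unexposed at the moment of ordering: at control sites the screen still shows the old default, whichever orderset is opened. On that reading the two sections agree. The resident check and spillover analysis also show that the authors did not assume carry-over away. This stands too: section 6 needs clarification, not retraction.

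**Location is itself a proxy.** Only someone who opens the orderset, at the relevant option, sees the default. Section 6 describes its users as the pediatric service and lists a separate M-POP option. A general-service prescriber at Mott might never see the new setting. This stands, but location is a necessary condition for meeting the default on screen; service and role are not.

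**Other analyses help.** Pediatric-service patients outside Mott do bear on whether the default carries over to sites showing the old one, so they inform k. They do not identify or remove any control prescription.

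**Needless flagging is minor.** It requires a resident whose pediatric-service prescribing was all outside Mott after the intervention. It costs data but leaves no exposed control in.

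**Conclusion.** The mismatch between the rule and the display condition is certain from the text. Its consequence is conditional: prescriptions by exposed prescribers can stay in the control group, unseen by the check, and would then bias the prescribing effect toward zero if habits carry over.

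The size is unknown. The table above ranges from a 2.5% to a 30% loss of the effect, but m and k are assumed throughout, and so is the even split behind the patient counts. These figures concern only the missed share. A figure based on all exposed control prescribers would overstate the defect, because dual-service residents are caught by the planned rule.

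This is a worthwhile correction to one sensitivity analysis and to one statement in section 6. It does not show that the main estimate is contaminated.

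**What to change.** 1. **Section 10, contamination check.** Flag any prescriber (attending, resident or other) who on or after October 1, 2020 wrote a post-tonsillectomy opioid prescription for a Mott patient aged 12 or older, on either service and whether or not that patient is in the analysis set. Where MiChart records it, require that the prescription came through the new orderset. Exclude that prescriber's control-group prescriptions after the first such date, and report the number removed.
2. **Section 6.** State that control clinicians are unexposed when ordering for control-site patients but may have met the new default at Mott.
3. **Section 10, spillover analysis.** Report general-service patients at Mott as treated where the new orderset displays, separately from pediatric-service patients outside Mott, who show carry-over.

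The cost is wording plus prescriber and location fields. The plan already needs both, for the clinician fixed effects and for group assignment. The extra work is to identify Mott prescriptions outside the analysis set.

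There are three downsides, all confined to a sensitivity analysis. Some control prescriptions are lost. Writing at Mott remains an imperfect sign of having seen the default. Dropping only a prescriber's later prescriptions can also shift the prescriber mix between periods, so the result is best read beside the version with clinician fixed effects.
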